6.5.3.3. Dose Reductions

Dose reduction is defined as actual non-zero dose < 90% of the planned dose.

Number and percentage of patients with at least one dose reduction as well as a breakdown of dose reductions (1, 2, 3, ≥ 4) will be summarized.

6.5.3.4. Dose Delays

Dose Delay is the difference between the actual time between two consecutive non-zero doses and the planned time between the same two consecutive non-zero doses.

Dose Delay for Dose x (days) = Date of Dose x – Date of Dose (x-1) – Planned days between two consecutive doses.

Dose delays will be grouped into the following categories.

- No delay;
- 1-2 days delays;
- 3-6 days delay;

- 7 or more days delay.

No delay and 1-2 days delay will also be summarized together.

For example, for PF-05082566, administered on a 4-week schedule, if one patient receives PF-05082566 on Day 1, then the next PF-05082566 administration date will be on Day 29; however, if the patient receives PF-05082566 at Day 30 or 31, this is considered as 1-2 days delay.

Number and percentage of patients with delayed study drug administration and maximum length of delay, ie, the worst case of delay if patients have multiple dose delays will be summarized.

6.5.3.5. Infusion Rate Reductions

The number and percentage of patients with at least one infusion rate reduction of 50% or more compared to the first infusion rate reported in the eCRF (first entry on the first dosing record page) as well as the frequency of patients with 1, 2, 3 or ≥ 4 infusion rate reductions of 50% or more will be summarized.

6.5.3.6. Infusion Interruptions

An infusion interruption is defined as an infusion that is stopped and re-started on the same day (ie, for a visit more than one infusion start time and infusion end time are recorded).

The number and percentage of patients with at least one infusion interruption as well as the frequency of patients with 1, 2, 3, or ≥ 4 infusion interruptions will be summarized.

6.5.4. Concomitant Medications and Non-Drug Treatments

The following analyses will be based on the safety analysis set by treatment group.

Concomitant medications are medications, other than study medications, which started prior to first dose date of study treatment and continued on on-treatment period as well as those started during the on-treatment period. **Prior medications** are medications, other than study medications and pre-medications for study drug, which are started before the first dose of study treatment.

Prior and concomitant medications will be summarized from the 'Prior and Concomitant Drug/Non-Drug Treatment' eCRF page.

Summary of prior and concomitant medications will include the number and percentage of patients by Anatomical Therapeutic Chemical (ATC) Classification level 2 and preferred term. A patient will be counted only once within a given drug class and within a given drug name, even if he/she received the same medication at different times. If any prior or concomitant medication is classified into multiple ATC classes, the medication will be summarized separately under each of these ATC classes. The summary tables will be sorted on decreasing frequency of drug class and decreasing frequency of drug name in a given drug class. In case of equal frequency regarding drug class (respectively drug name), alphabetical order will be used. In case any specific medication does not have ATC classification level 2 coded term, it will be summarized under 'Unavailable ATC classification' category.

A listing of concomitant medications will be created with the relevant information collected on the 'Prior and Concomitant Drug Treatment' eCRF page.

A listing of concurrent procedures will be created with the relevant information collected on the 'Prior and Concomitant Non-Drug Treatment' eCRF page.

6.5.5. Subsequent Anti-cancer Therapies

The following analyses will be based on the FAS by treatment group.

Anti-cancer treatment will be provided in a data listing with data retrieved from 'Follow-up Systemic Therapy – for Cancer', 'Concomitant Radiation', and 'Concomitant Surgery' eCRF pages. The earliest date of start of new anti-cancer drug therapy after first dose of study treatment will be used for the definition of the on-treatment period and the earliest date of start of new anti-cancer therapy after first dose of study treatment will be used for the censoring for efficacy analyses (see [Sections 5.2.5](#) and [5.2.6](#)).

Number and percentage of patients with any anti-cancer therapy after discontinuation will be tabulated based on the data collected from the 'Follow-up Systemic Therapy – for Cancer' eCRF page.

6.6. Safety Summaries and Analyses

The Safety Analysis Set will be the primary population for safety evaluations. Summaries of AEs and other safety parameters will be based on the safety analysis set by treatment group.

Summaries of related AEs (PF-05082566 plus mogamulizumab) may further be presented as PF-05082566-related, mogamulizumab -related, or related to both study treatments.

All summaries described below by SOC and PT will further be presented by PT in decreasing frequency based on the frequencies observed in all treatment groups combined.

6.6.1. Adverse Events

Treatment-emergent adverse events (TEAEs) are those events with onset dates occurring during the on-treatment period for the first time, or if the worsening of an event occurs during the on-treatment period as defined in [Section 3.5.1](#).

All analyses described will be based on TEAEs (started during the on-treatment period) if not otherwise specified. The AE listings will include all AEs (whether treatment-emergent or not). AEs outside the on-treatment period will be flagged in the listings.

- **Related Adverse Events:** adverse events with relationship to study treatment (as recorded on the AE eCRF page, Relationship with study treatment = Related) reported by the investigator and those of unknown relationship (ie, no answer to the question 'Relationship with study treatment').
- **Serious Adverse Events (SAE):** serious adverse events (as recorded on the AE eCRF page, Serious Adverse Event = Yes).

- **Adverse Events Leading to Permanent Treatment Discontinuation:** adverse events leading to permanent discontinuation of study treatment (as recorded on the AE eCRF page, Action taken with study treatment = Drug withdrawn).
- **Adverse Events Leading to Death:** adverse event leading to death (as recorded on the AE eCRF page, Outcome = Fatal, as well as AEs of Grade 5).
- **Immune-related Adverse Events (irAE):** irAEs (as identified by clinical review based on the SRP prior to DB lock).
- **Infusion-related Reactions (IRR):** IRRs (as identified by clinical review based on the SRP prior to DB lock) with onset on study drug dosing date (not prior to infusion of study drug) or the day following study drug infusion.

Unless otherwise specified, AEs will be summarized by number and percentage of patients with the AE in the category of interest as described above, by treatment group, primary SOC and PT in decreasing frequency observed in all treatment groups combined.

Each patient will be counted only once within each SOC or PT. If a patient experiences more than one AE within a SOC or PT for the same summary period, only the AE with the strongest relationship or the worst severity, as appropriate, will be included in the summaries of relationship and severity.

6.6.1.1. All Adverse Events

Adverse events will be summarized by worst severity (according to NCI-CTCAE version 4.03) per patient, using the latest version of MedDRA preferred term (PT) as event category and MedDRA primary system organ class (SOC) body term as Body System category.

In case a patient has events with missing and non-missing grades, the maximum of the non-missing grades will be displayed. No imputation of missing grades will be performed.

The following tables will be created:

- The overall summary of AEs table will include the frequency (number and percentage) of patients with each of the following by treatment group:
 - TEAEs;
 - TEAEs, Grade ≥ 3 ;
 - Related TEAEs;
 - Related TEAEs, Grade ≥ 3 ;
 - TEAEs leading to permanent treatment discontinuation;
 - Related TEAEs leading to permanent treatment discontinuation;

- Serious TEAEs;
- Related Serious TEAEs;
- TEAEs leading to death;
- Related TEAEs leading to death;
- irAEs;
- Related irAEs;
- IRRs;
- Related IRRs.

- TEAEs by SOC and PT and worst grade;
- Related TEAEs by SOC and PT and worst grade;
- TEAEs leading to death by SOC and PT;
- Related TEAEs leading to death by SOC and PT;
- TEAEs by SOC and PT: displaying in separate columns the All TEAEs / Related TEAEs / Grade ≥ 3 TEAEs / Related Grade ≥ 3 TEAEs;
- TEAEs Excluding SAEs, with frequency $\geq 5\%$ in any treatment group by SOC and PT.

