9.6.2. Analysis of Secondary Safety Endpoints

9.6.2.1. Adverse Events

AEs will be graded by the investigator according to CTCAE version 4.03 and coded using the Medical Dictionary for Regulatory Activities (MedDRA). The focus of AE summaries will be on Treatment Emergent Adverse Events, those with initial onset or increasing in severity after the first dose of study medication. The number and percentage of patients who experienced any AE, SAE, treatment related AE, and treatment related SAE will be summarized according to worst toxicity grades. The summaries will present AEs both on the entire study period and by cycle (Cycle 1, Cycle 2 and Cycles >2).

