9.6.2.2. Laboratory Tests Abnormalities

The number and percentage of patients who experienced laboratory test abnormalities will be summarized according to worst toxicity grade observed for each lab assay. The analyses will summarize laboratory tests both on the entire study period and by cycle (Cycle 1, Cycle 2 and Cycles >2). Shift tables will be provided to examine the distribution of laboratory toxicities.

For laboratory tests without CTC grade definitions, results will be categorized as normal, abnormal or not done.

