5.2.7. Definition of On-treatment Period

Safety endpoints will be summarized based on the on-treatment period unless otherwise specified.

On-treatment period is defined as the time from the first dose of study treatment through minimum (30 days + last dose of study treatment, start day of new anti-cancer drug therapy – 1 day).

Safety data collected outside the on-treatment period as described above will be listed and flagged in listings but not summarized.

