6.6.5. Laboratory Data

6.6.5.1. Hematology and Chemistry Parameters

Laboratory results will be classified according to the NCI-CTCAE criteria version 4.03. Non-numerical qualifiers (with the exception of fasting flags) will not be taken into consideration in the derivation of CTCAE criteria (eg, hypokalemia Grade 1 and Grade 2 are only distinguished by a non-numerical qualifier and therefore Grade 2 will not be derived). Additional laboratory results that are not part of NCI-CTCAE will be presented according to the categories: below normal limit, within normal limits and above normal limit (according to the laboratory normal ranges).

Quantitative data will be summarized using simple descriptive statistics (mean, SD, median, Q1, Q3, minimum, and maximum) of actual values and changes from baseline for each nominal visit over time (unscheduled measurements would therefore not be included in these summaries as described in [Section 5.2.9](#)). End of Treatment visit laboratory results will be summarized separately. The changes computed will be the differences from baseline. Qualitative data based on reference ranges will be described according to the categories (ie, Low, Normal, High).

Abnormalities classified according to NCI-CTCAE toxicity grading version 4.03 will be described using the worst grade. For those parameters which are graded with two toxicities such as potassium (hypokalemia/hyperkalemia), the toxicities will be summarized separately. Low direction toxicity (eg, hypokalemia) grades at baseline and post baseline will be set to 0 when the variables are derived for summarizing high direction toxicity (eg, hyperkalemia), and vice versa.

For **WBC differential counts** (total neutrophil [including bands], lymphocyte, monocyte, eosinophil, and basophil counts), the absolute value will be used when reported. When only percentages are available (this is mainly important for neutrophils and lymphocytes, because the CTCAE grading is based on the absolute counts), the absolute value is derived as follows:

$$\text{Derived differential absolute count} = (\text{WBC count}) \times (\text{Differential \%value} / 100)$$

If the range for the differential absolute count is not available (only range for value in % is available) then Grade 1 will be attributed to as follows:

- Lymphocyte count decreased:
 - derived absolute count does not meet Grade 2-4 criteria, and
 - % value < % LLN value, and
 - derived absolute count $\geq 800/\text{mm}^3$.

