- peak serum ALT(/ULN) vs peak total bilirubin (/ULN) including reference lines at ALT=3×ULN and total bilirubin =2×ULN.
- peak serum AST(/ULN) vs peak total bilirubin (/ULN) including reference lines at AST=3×ULN and total bilirubin =2×ULN.

In addition, a listing of all TBILI, ALT, AST and ALP values for patients with a post-baseline TBILI $\geq 2 \times$ ULN, ALT $\geq 3 \times$ ULN or AST $\geq 3 \times$ ULN will be provided.

Parameters with NCI-CTC grades available:

The laboratory toxicities will be tabulated using descriptive statistics (number of patients and percentages) during the on-treatment period. The denominator to calculate percentages for each laboratory parameter is the number of patients evaluable for CTCAE grading (ie, those patients for whom a Grade 0, 1, 2, 3 or 4 can be derived).

- The summary of laboratory parameters by CTCAE grade table will include number and percentage of patients with Grade 1, 2, 3, 4, Grade 3/4 and any grade(Grades 1-4), laboratory abnormalities during the on-treatment period.
- The shift table will summarize baseline CTCAE grade versus the worst on-treatment CTCAE grade. The highest CTCAE grade during the on-treatment period is considered as the worst grade for the summary.

The above analyses apply to hematology and chemistry evaluations which can be graded per CTCAE, ie:

- Hematology:

Hemoglobin (HB), Leukocytes (white blood cell decreased), Lymphocytes (lymphocyte count increased/decreased), Neutrophils / Absolute Neutrophils Count (ANC) (neutrophil count decreased), Platelet Count (PLT) (platelet count decreased), Coagulation (activated partial thromboplastin time (aPTT) and prothrombin time (INR)).

- Serum Chemistry:

Albumin (hypoalbuminemia), Alkaline Phosphatase (alkaline phosphatase increased), Alanine Aminotransferase (ALT) (ALT increased), Amylase (serum amylase increased), Aspartate Aminotransferase (AST) (AST increased), Total Bilirubin (blood bilirubin increased), Cholesterol (cholesterol high), Creatinine (creatinine increased), Creatine Kinase (CPK increased), Potassium (hypokalemia/ hyperkalemia), Sodium (hyponatremia/ hypernatremia), Magnesium (hypomagnesemia/hypermagnesemia), Calcium (hypocalcemia/ hypercalcemia), Glucose (hypoglycemia/hyperglycemia), Gamma Glutamyl Transferase (GGT) (GGT increased), Lipase (lipase increased), Phosphates (hypophosphatemia), Triglycerides (hypertriglyceridemia).

Parameters with NCI-CTC grades not available:

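### The SAP omits the protocol's by-cycle adverse event and laboratory-grade summaries, leaving only crude rates over an on-treatment window of variable length

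*SAP*

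**What the plan says.** **Protocol.** Section 9.6.2.1 states: "The summaries will present AEs both on the entire study period and by cycle (Cycle 1, Cycle 2 and Cycles >2"). Section 9.6.2.2 makes the same commitment for laboratory abnormalities by worst grade: "The analyses will summarize laboratory tests both on the entire study period and by cycle (Cycle 1, Cycle 2 and Cycles >2").

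**SAP, period.** Section 5.2.7 sets the default: "Safety endpoints will be summarized based on the on-treatment period unless otherwise specified". It continues: "On-treatment period is defined as the time from the first dose of study treatment through minimum (30 days + last dose of study treatment", or to the day before new anti-cancer drug therapy if that is earlier.

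**SAP, adverse events.** Section 6.6.1 says that "AEs will be summarized by number and percentage of patients with the AE in the category of interest as described above, by treatment group". The table lists in 6.6.1.1 (for example "TEAEs by SOC and PT and worst grade"), 6.6.1.2, 6.6.3 and 6.6.4 contain no AE incidence table by cycle and none adjusted for exposure.

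**SAP, laboratory grades.** Section 6.6.5.1 tabulates grades over the on-treatment period, and for the shift table: "The highest CTCAE grade during the on-treatment period is considered as the worst grade for the summary".

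**What the SAP keeps on a common time scale.** DLTs in the first two cycles are summarised by treatment group (3.1, 6.1.1.1). Quantitative laboratory data are given as "actual values and changes from baseline for each nominal visit over time" (6.6.5.1). First onset of an infusion-related reaction is tabulated by infusion number (6.6.4). Treatment duration is summarised for each drug (6.5.3).

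**The concern.** The on-treatment period is set by how long each patient stays on drug. It runs from about one month after a single dose to about 25 months for a patient who completes 24 months of treatment. A crude percentage over such a window reflects both the risk per unit time and the time at risk. A dose level whose patients stay on longer will show more events and worse grades even if the risk per cycle is the same. A dose level whose patients progress early will look safer.

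Time on treatment could plausibly differ by dose level. Under Protocol 3.1.1 the 100 mg flat-dose cohort takes only SCCHN and/or squamous NSCLC, and the 5.0 mg/kg cohort is to enrol at least 6 squamous NSCLC patients. Under Protocol 4.1 the other dose-finding levels are also open to CRC, bladder and ovarian tumours.

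The stake is how readable the secondary safety comparison between dose levels is. The protocol's by-cycle tables would have given that comparison a common window.

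**Working it through.** **1. The plan's own figures.** Neither document gives a figure on this point. The one numerical safety statement is that 30 patients detect a 5% or 10% toxicity with probability 0.79 or 0.96. It reproduces: 1 − 0.95^30 = 0.785 and 1 − 0.90^30 = 0.958. It does not bear on window length.

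**2. Inputs.** From the documents: treatment up to 24 months (taken as 730 days) and a window ending 30 days after last dose. Assumed, because the documents do not give them: a constant risk r per 28 days, equal at every dose, and exponential time on treatment with a median of w weeks. New anti-cancer therapy within the 30 days is ignored.

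**3. Formula.** Let λ = −ln(1 − r)/28 and μ = ln 2/(7w) per day. With follow-up T = min(time on treatment, 730) + 30, crude incidence is

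1 − e^(−30λ) × [ μ/(μ+λ) × (1 − e^(−730(μ+λ))) + e^(−730(μ+λ)) ].

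**4. Numbers at r = 10%.** λ = 0.003763 and e^(−30λ) = 0.8933.

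- Median 8 weeks: μ = 0.012378, bracket 0.7669, incidence 1 − 0.8933 × 0.7669 = 31.5%.
- Median 16 weeks: μ = 0.006189, bracket 0.6222, incidence 1 − 0.8933 × 0.6222 = 44.4%.
- Median 24 weeks: μ = 0.004126, bracket 0.5245, incidence 1 − 0.8933 × 0.5245 = 53.1%.

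| Risk per 28 days | 8 weeks | 16 weeks | 24 weeks |
|---|---|---|---|
| 5% | 18% | 27% | 34% |
| 10% | 32% | 44% | 53% |
| 20% | 52% | 66% | 73% |

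At 10%, the gaps from the 8-week group are about 13 and 22 points with no difference in risk.

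**5. Early clustering.** If the 10% hazard falls to one third after week 8, the three rates become 23%, 30% and 35%. The largest gap shrinks from 22 to 12 points.

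**6. Fixed durations.** For a patient treated for c ≥ 2 cycles, with the last mogamulizumab dose on Day 15, the window is 28(c − 1) + 14 + 30 days: 72 days for 2 cycles, 184 for 6 and 352 for 12. With hazard h per 28 days, incidence is 1 − e^(−h × days/28).

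- h = 0.05: 12.1%, 28.0% and 46.7%.
- h = 0.10: 22.7%, 48.2% and 71.6%.

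For 6 patients at h = 0.10, that is 6 × 0.227 = 1.4 expected patients with the event after 2 cycles, against 6 × 0.482 = 2.9 after 6 cycles.

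**7. Effect of the by-cycle tables.** At equal hazard the Cycle 1 rate is 1 − e^(−h): 4.9% at h = 0.05 and 9.5% at h = 0.10, whatever the total duration. Cycle 2 behaves the same among patients who start it. Cycles >2 does not. At h = 0.10, 4 cycles leave 128 − 56 = 72 days and 22.7%, while 12 cycles leave 352 − 56 = 296 days and 65.3%.

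**The case against.** **The SAP may change secondary analyses.** Protocol section 9 and SAP section 2 both say so, and an amendment is needed only for major changes to the primary endpoint or its analysis. This stands: the omission is permitted, but unexplained. The silence of the SAP's change table adds little, since nothing shows that an earlier SAP contained these tables.

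**Dose selection does not depend on these tables.** A reader might infer that the MTD or RP2D would be biased. The documents do not support that. The MTD comes from DLTs over a common 8-week window, and the RP2D is anchored to the MTD (Protocol 3.3, 3.6). The steering committee can weigh lower-grade events and their timing during escalation (Protocol 9.7). Long-term feasibility, to which whole-period data are relevant, also enters the RP2D.

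**The information is partly available elsewhere.** All AEs are listed and relevant listings show study day. Treatment duration is tabulated, and cohorts have 3 to 9 evaluable patients. A reader could reconstruct timing patient by patient, but none of this gives AE or grade rates in a common window.

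**The size is hypothetical.** No document gives time on treatment by dose. SCCHN and squamous NSCLC may also enrol at every dose-finding level. On timing, Protocol 1.2.3 points both ways: in the earlier study's rituximab portion, related events fell mostly in the first two cycles, while the single-agent portion showed no significant difference between periods. Sampling noise is also larger than the distortion. The standard error of a difference between 31.5% and 44.4% is √[(0.315×0.685 + 0.444×0.556)/6] = 0.28 with 6 patients per group, and 0.23 with 9. These points limit the weight of the concern. They do not remove a systematic effect that the promised tables would largely avoid in Cycles 1 and 2.

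**Comparison with the earlier study.** A reader might infer that the omission blocks a planned comparison, because Protocol Tables 4 and 5 are split into Cycles 1-2 and Cycles >2. Neither document plans an AE comparison with that study; the planned historical comparison concerns PK and anti-drug antibodies. Those tables also use all-patient denominators (40 and 27).

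**Conclusion.** The protocol commits to by-cycle AE and laboratory-abnormality summaries. The SAP's AE incidence and laboratory-grade tables do not deliver them, offer no exposure-adjusted replacement and give no reason.

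It would be wrong to conclude that every SAP safety table has this weakness. DLTs, continuous laboratory values by visit and infusion-reaction onset by infusion number are not whole-period crude rates. The gap is limited to descriptive secondary safety data, with no hypothesis test.

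Within that limit the distortion can be material: about 13 to 22 points at a constant 10% risk per 28 days and median durations of 8 against 16 or 24 weeks. It falls to about 7 to 12 points if the hazard drops to one third after week 8. It vanishes if time on treatment is the same across dose levels. Unequal duration is an assumption, plausible from the tumour-type restrictions but not shown in the documents. The change is worth making because the protocol already promises the tables and they cost little.

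**What to change.** In SAP 6.6.1.1 and 6.6.5.1, add summaries by Cycle 1, Cycle 2 and Cycles >2 for TEAEs, related TEAEs, Grade ≥3 TEAEs and worst laboratory grade. The denominator should be patients starting each cycle and, for Cycles >2, patients starting Cycle 3. Use the Cycle 1 and Cycle 2 tables for descriptive comparison between dose levels, and keep the whole-period tables for the overall profile. Add a note that Cycles >2 still mixes unequal exposure and should be read alongside treatment duration.

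One rule needs stating. SAP 6.5.3 ends the last cycle 28 days after it starts, whereas the on-treatment period runs 30 days past the last dose. With a last mogamulizumab dose on Day 15, events can fall up to 15 + 30 − 28 = 17 days after that cycle ends. The SAP should say where these are counted.

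If the sponsor prefers not to produce the tables, the SAP should record the departure from the protocol and the reason.

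Cost: SAP wording and reruns of existing tables with a period variable. Cycle start and end dates are already derived in SAP 6.5.3, and no new data are needed. The downside is a few more tables with small counts.
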